4.2 Key Secondary Endpoint, Double-Blind Period

Disease progression

• as assessed by longitudinal changes from baseline in the modified UMSARS Part I (mUMSARS) score up to EoTDB

4.3 Secondary Endpoints, Double-Blind Period

Disease progression

• as assessed by longitudinal changes from baseline in the UMSARS Part I, and UMSARS Part II scores up to EoTDB

Function

- Change from baseline to Week 48 in UMSARS TS
- Change from baseline to Week 48 in UMSARS Part I score
- Change from baseline to Week 48 in mUMSARS score
- Change from baseline to Week 48 in UMSARS Part II score
- Change from baseline to Week 48 in Schwab and England Activities of Daily Living scale (SE-ADL)

Global impression

- Change from baseline to Week 48 in Clinical Global Impression Severity (CGI-S) score
- Change from baseline to Week 48 in Patient Global Impression Severity (PGI-S) score
- Change from baseline to Week 48 in Observer-reported Global Impression Severity of Illness (OGI-S)

Autonomic symptoms

• Change from baseline to Week 48 in Composite Autonomic Symptom Score Select Change (COMPASS Select Change) score

Global disability

• Change from baseline to Week 48 in UMSARS Part IV score

Disease milestones

- Change from baseline to Week 48 in speech, swallowing, falls, and walking, as assessed by the UMSARS Part I sub-items
- Change from baseline to Week 48 in frequency, cause and consequence of falls, as assessed by the fall diary in dedicated periods

Health-related quality of life

• Change from baseline to Week 48 in EQ-5D-5L score (individual items and VAS score)

MRI biomarkers

• Percentage change from baseline to Week 48 in brain volume in brain regions-of-interest (ROIs); primary ROIs: pons and cerebellum; secondary ROIs: caudate nucleus, putamen, brain stem and total grey matter, as measured by volumetric MRI (vMRI)

Biofluid biomarkers

• Blood: Change from baseline up to Week 48 in neurofilament light chain (NfL) concentrations

Pharmacokinetics

- Lu AF82422 plasma concentration during treatment and safety follow-up
- Lu AF82422 cerebrospinal fluid (CSF) concentrations and the CSF/plasma concentration ratios

4.4 Safety Endpoints

4.4.1 Double-Blind Period

- Treatment emergent adverse events
- Absolute values and changes from baseline in clinical safety laboratory test values, vital signs, weight, and ECG parameter values
- Development of specific anti-drug antibodies (ADA)
- Findings on MRI, as specified in the *Imaging Charter*
- Columbia-Suicide Severity Rating Scale (C-SSRS) score

4.4.2 **Open-label Extension Period**

- Treatment-emergent adverse events
- Absolute values and changes from baseline in clinical safety laboratory test values, vital signs, and weight parameter values
- Development of specific anti-drug antibodies (ADAs)
- Columbia-Suicide Severity Rating Scale (C-SSRS) score

4.5 Exploratory Endpoints

4.5.1 Double-Blind Period

Disease progression

• as assessed by longitudinal changes from baseline in the abbreviated UMSARS (aUMSARS) score up to EoTDB

Function

• Changes from baseline to Week 48 in aUMSARS

Autonomic symptoms

• Change from baseline to Week 48 in heart rate, blood pressure, and orthostatic symptoms, as assessed in UMSARS Part III

Disease milestones

- Time to wheelchair use, as assessed by the recording of wheelchair use in the physical examination CRF Form
- Change from baseline to Week 48 in frequency of falls, as assessed by PamSys device
- Change from baseline to Week 48 in gait parameters, as assessed by FeetMe device

MRI biomarkers

- Percentage change from baseline to Week 48 in cerebral blood flow in ROIs; putamen and cerebellum, as measured by arterial spin labelling (ASL) MRI
- Percentage change from baseline to Week 48 in tissue integrity in ROIs; primary ROIs: putamen, cerebellar cortex and white matter; secondary ROIs: caudate nucleus, globus pallidus and middle cerebellar peduncle, as measured by diffusion-tensor imaging (DTI) MRI

Blood/CSF biomarkers

- CSF: Change from baseline up to Week 48 in t-tau and NfL concentrations
- CSF: Concentrations of 'free' and 'total' α-synuclein at baseline and Week 48
- CSF: Changes from baseline up to Week 48 in pathological species of α-synuclein
- Blood: Plasma concentrations of 'free' and 'total' α-synuclein during treatment and safety follow-up

4.5.2 **Open-label Extension Period**

Effect on long-term treatment:

- Change from baseline of the DBP and baseline of the OLE to End-of-Treatment of the OLE (EoTOLE) in UMSARS TS and mUMSARS score
- Change from baseline of the DBP and baseline of the OLE to EoTOLE in CGI-S score
- Change from baseline of the DBP and baseline of the OLE to EoTOLE in PGI-S score
- Change from baseline of the DBP and baseline of the OLE to EoTOLE in SE-ADL score
- Change from baseline of the DBP and baseline of the OLE to EoTOLE in health-related quality of life, as assessed using EQ-5D-5L score
- Percentage change from baseline of the DBP and baseline of the EoTOLE in brain atrophy in ROIs, as measured using vMRI
- Change from baseline of the DBP and baseline of the OLE to EoTOLE in blood NfL concentrations

5 Analysis Sets

The patients will be assigned to analysis sets based on IMP intake and post-baseline assessments of the primary efficacy variable in the Treatment Period.

The following analysis sets will be used for the analyses:

- *all-patients-randomized set* (APRS) all randomized patients
- *all-patients-treated set* (APTS) all patients in the APRS who took at least one dose of double-blind IMP
- *full-analysis set* (FAS) all patients in the APTS who had a valid baseline assessment and at least one valid post-baseline assessment of the UMSARS TS, prior to, or at withdrawal from treatment
- *PK sub-set* (PKS) all patients in the APTS with quantifiable plasma or CSF concentration of Lu AF82422
- *Sensor-based subset* (SBS) all patients in the APTS who consented to wear at least one of the included sensor-based devices and who had a valid baseline assessment and at least one valid post-baseline assessment, where 'valid assessment' covers that gait parameters can be derived within the observation period
- *Exit Interview subset* all patients in the FAS having a complete Exit interview with the patient and/or the caregiver
- *Study Experience subset* all patients in the FAS having a complete Study Experience interview with the patient and/or the caregiver
- *Open-label treatment extension set* (OLES) all patients in the FAS who consented to participate in the OLE and who had at least one dose of Open-Label IMP for the OLE

All data from the Placebo-controlled Period will be cleaned and the database for the DB-Period will be locked when there are no more patients in the DB-Period. The patients and data will be classified into the analysis sets according to these definitions at a Classification Meeting held after the database containing all efficacy measures from the DB-Period has been released but before unblinding of the study.

Demographics, baseline characteristics and baseline efficacy variables will be summarized based on the APTS and on the OLES, respectively.

The efficacy analyses for the DB-Period will be based on the FAS. Analyses for the Extension Period will be based on the OLES.

Safety outputs (including exposure and concomitant medications) will be based on APTS in the DB-Period and OLES for the Extension Period, respectively. Relevant safety outputs for data collected during the Safety Follow-up Period for participants not entering the OLE will be based on the APTS.

Listings will be based on the APTS.

6 Descriptive Statistics

Unless otherwise specified, summary statistics (n, arithmetic mean, standard deviation [SD], median, lower and upper quartiles, minimum and maximum values) will be presented for continuous variables, and counts and, if relevant, percentages will be presented for categorical variables. Shift-tables will be presented for categorical variables where specified.

Unless otherwise specified, data listings will include site, treatment group, patient number, sex, age, region and race.

7 Patient Disposition

7.1 Summary of Patient Disposition

Patient disposition will be summarized overall and by region. Summaries will include the number of patients in each analysis set defined in chapter 5, and the number of patients in the APTS who completed or withdrew from study.

The number of patients with a completed OLE and Safety Follow-up visit will be presented.

7.2 Withdrawals

The number of patients who withdrew from the study will be summarized by primary reason for withdrawal and all reasons for withdrawal by period.

If relevant, Kaplan-Meier failure plots of time to withdrawal will be presented by treatment group for the DB-Period. The time will be calculated from the date of first dose of IMP to the date of withdrawal in the DB-Period. Patients who completed the DB-Period according to their individual treatment duration (48-72 weeks) will be regarded as censored at the End of treatment visit.

Patients who withdrew from the study will be listed and the listing will include the number of days in the study until withdrawal, the number of days on IMP, the primary reason for withdrawal, and all reasons for withdrawal.

All tables, graphs, and listings will be based on the FAS.

8 Demographics and Baseline Characteristics

Demographics (sex, age, race, region), Screening MRI findings supporting MSA diagnosis and CCI ; baseline disease characteristics (incl. MSA sub-type, CSF/blood NfL level, result from the qualitative alpha-synuclein seeding assay (SAA), time since symptom onset and diagnosis); baseline physical examinations and baseline efficacy variables will be summarized by treatment group and overall. Concurrent as well as relevant past medical and psychiatric disorders will be coded using the *Medical Dictionary for Regulatory Activities* (MedDRA) and summarized.

A concurrent medical or psychiatric disorder is a disorder that is ongoing at the baseline Visit. A past medical or psychiatric disorder is a disorder that ended prior to the baseline Visit.

Demographics and baseline characteristics will be summarized based on the APTS, PKS and SBS, and baseline efficacy variables will be summarized based on the FAS.

9 Recent and Concomitant Medication

Recent and concomitant medication will be coded using the *WHO Drug Dictionary* (WHO-DDE).

Medications will be classified according to the start and stop time and summarized by anatomical therapeutic chemical (ATC) code, and generic drug name:

- medication discontinued prior to first dose of IMP
- concomitant medication continued after first dose of IMP
- concomitant medication started at or after first dose of IMP

In addition, concomitant medications continued or started after first dose of IMP will classified into two overall groups depending on purpose, i.e., treatment of motor symptoms ('anti-Parkinson medication') and treatment of autonomic dysfunction ('Autonomic dysfunction medication'). The classification will be done prior to unblinding according to Protocol Appendix VII.

The tables will be based on the APTS.

10 Exposure

For each infusion visit, information related to infusion completed as planned (yes/no), infusion temporarily interrupted (yes/no), and infusion lasted longer than 30 (+10) minutes (yes/no), as well as descriptive statistics for the duration of infusions (this duration includes duration of any infusion interruptions) and duration of temporary interruptions will be summarized by treatment group for the DB-Period and the OLE-Period, respectively.

Patients, who at any point during the study received a different dose than what was planned, will be listed for each period. The listing will include date of infusion visit, planned dose for the patient and actual dose received for the patient.

Exposure (days) to IMP will be calculated as:

(Date of last dose + 28 days) – Date of first dose + 1

Exposure to IMP will be summarized in weeks using descriptive statistics.

Study 18331A - Statistical Analysis Plan

Patient years of exposure (PYE) will be calculated as the sum of the number of days of exposure to IMP for each patient, divided by 365.25 days.

The number and percentage of patients with different durations of exposure (≤ 4 weeks, >4 to ≤ 8 weeks, >8 to ≤ 12 weeks, ..., >68 to ≤ 72 weeks) will be presented.

Exposure will be summarized based on the APTS. In addition, all infusion data will be listed.

11 Fall Diary Compliance

The Fall Diary is planned to be dispensed and filled out in 5 periods during the study, i.e., at a two-week Baseline period and at four post-baseline four-week periods, respectively. For each period, days where the fall diary has been missed will be summarized and presented by period and treatment group. Furthermore, the number of patients missing 7 days or more (at Baseline and at subsequent periods) and 14 days or more (at subsequent periods) in each period will be presented by period and treatment group.

A day where the fall diary has been missed is defined as a day where the subject did not fill out anything in the diary.

The summaries will be based on the FAS.

12 Wearable Compliance

For both Baseline and the DB-Period, compliance is evaluated as number of days used for each of the two wearables, i.e., FeetMe and PanSys, which will be summarized within each interval where applied and treatment group. Furthermore, the number of patients missing 7 days or more and 14 days or more in a 28-day period will be presented by interval and treatment group. The following intervals will be evaluated:

- BL interval: V2 to V3 (2 weeks)
- Interval 1: V7 to V9 (4 weeks)
- Interval 2: V10 to V11 (4 weeks)
- Interval 3: V13 to V14 (4 weeks)
- Interval 4: V17 to V18 (4 weeks)

Records outside the above predefined intervals will be included as long as they can be mapped to one of the above intervals according to the defined visit windows (See section 24.2). Individual wearable data will be mapped to the end visit defining each interval, corresponding to the visit where the wearable is handed back.

The summaries will be based on the SBS.

13 Primary Estimand

The following primary estimand is defined as:

Proposed handling of IE's

For evaluating the appropriateness of this overall strategy, a number of sensitivity analyses will be performed using different imputation strategies for missing data. For additional information see section 14.3.5: Sensitivity Analyses of the Primary Endpoint, also covering sensitivity analyses for the key Secondary Endpoint.

Key Secondary Estimand

A key secondary study estimand will be defined in a similar manner with the endpoint of interest being the CCI

14 Efficacy

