#### 6.4 Withdrawal Criteria

A patient must be withdrawn from the study if:

- The patient withdraws consent (defined as a patient **explicitly** takes back his or her consent); section 9.6 states how the patient's data will be handled
- The patient has been randomized in error and has not been administered IMP
- Withdrawal of patients enrolled in error and who have received the IMP should be based on a case-by-case evaluation of the individual risk/benefit. The decision about the administration of more doses of Lu AF82422 will be based on an individual risk/benefit assessment as judged by the investigator
- The patient can no longer attend study visits due to MSA disease progression.
- The patient is lost to follow-up (defined as a patient who fails to comply with scheduled study visits or contact, who has not actively withdrawn from the study, and for whom no alternative contact information is available [this implies that at least two documented attempts have been made to contact the patient])

A patient must be withdrawn from treatment if:

- The patient experiences any systemic hypersensitivity reaction to IMP infusion which are confirmed as anaphylactic reaction by a clinically relevant increase of serum total tryptase from baseline level (see section 11.1.3)
- The patient experiences any severe and/or serious systemic hypersensitivity reactions even though the serum total tryptase does not confirm an anaphylactic reaction
- The patient experiences an adverse event that, in the opinion of the investigator or sponsor's medical expert, contraindicates further dosing
- The investigator considers it, for safety, lack of efficacy, and/or study compliance reasons, in the best interests of the patient that he or she be withdrawn from treatment
- Any site personnel breaks the randomization code for that patient
- The patient becomes pregnant
- The patient has a serum ALT or AST value >3 times the upper limit of the reference range and a serum total bilirubin value >2 times the upper limit of the reference range
- The patient has a serum ALT or AST value >5 times the upper limit of the reference range that is confirmed by testing <2 weeks later
- The patient has a QTcF interval >500 ms confirmed on repeat, if the repeat is done within 72 hours; the decision to withdraw the patient may be postponed until a repeat ECG is taken, if it is taken within 72 hours during the DBP.
- A patient may be withdrawn from the study if:

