# 17.3 Analysis Sets

The patients and data will be classified into the analysis sets according to these definitions at a *Classification Meeting* held after the study database has been released, but before the blind has been broken (except for the PK subset which will be classified after unblinding).

- all-patients-randomized set (APRS) all randomized patients
- all-patients-treated set (APTS) all patients in the APRS who received at least one dose of double-blind IMP
- *all-patients-treated-follow-up set* (APTS-FU) all patients in the APTS who complete the DBP and who has data collected up to and at the Safety Follow-up DBP Visit
- *full-analysis set* (FAS) all patients in the APTS who had a valid baseline assessment and at least one valid post-baseline assessment of the UMSARS Part I and Part II, prior to, or at withdrawal from treatment in the DBP
- *PK subset* (PKS) all patients in the APTS with quantifiable plasma or CSF concentration of Lu AF82422
- sensor-based subset (SBS) all patients in the APTS who consented to wear at least one of
  the included sensor-based devices and who had a valid baseline assessment and at least
  one valid post-baseline assessment
- exit interview subset (EIS) all patients in the FAS having a complete Exit interview with the patient and/or the caregiver
- *study experience interview subset* (SEIS) all patients in the FAS having a complete Study Experience interview with the patient and/or the caregiver
- *open-label treatment extension set* (OLES) all patients in the FAS who consented to participate in the OLE and who had at least one dose of open-label IMP for the OLE

The efficacy analyses will be based on the FAS and the OLES, and the safety analyses will be based on the APTS, APTS-FU, and the OLES unless otherwise specified. Listings will be based on the APRS.

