#### 17.5 Patient Disposition

Patient disposition will be summarized by period and treatment group and include the number of patients in the APTS who completed or withdrew from treatment, as well as the number of patients in each analysis set (APRS, APTS, FAS, PKS, SBS, EIS, SEIS, and OLES).

The number of patients who completed or withdrew from the study will also be summarized.

The number of patients who withdrew from treatment will be summarized by period and treatment group and primary reason for withdrawal as well as by treatment group and all reasons for withdrawal. A Kaplan-Meier plot will be presented for time-to-withdrawal for all reasons per treatment group, if appropriate.

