3.3 Definition of Withdrawal

The group of patients who withdrew from treatment at the scheduled visits in the Doubleblind Treatment Period will be described as *withdrawn from study*. This group will also contain randomized patients who withdrew from treatment prior to receiving any IMP and patients who died. The complementary group will be described as *completed study*. Patients who withdraw, except for those who withdraw their consent or died, will be asked to attend a Safety Withdrawal Visit 20 weeks after the last dose of IMP and undergo Safety Follow-Up evaluations.

Participants that drop out of the OLE will also undergo Safety Follow-Up evaluations according to trial procedures.

4 Endpoints

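### SAP 7.2 reports withdrawals on the FAS and so cannot show never-dosed or unassessed patients; separately, the SAP names two different sets for open-label safety outputs

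*SAP*

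**What the plan says.** **Withdrawals.** SAP 7.2 plans a summary of withdrawals by primary reason and by all reasons, a Kaplan-Meier plot timed from first dose, and a patient listing. It closes: "All tables, graphs, and listings will be based on the FAS". SAP chapter 5 defines the FAS as "all patients in the APTS who had a valid baseline assessment and at least one valid post-baseline assessment of the UMSARS TS"; an assessment made at withdrawal counts. The APTS itself requires a double-blind dose.

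SAP 3.3 defines the withdrawn group more widely: "This group will also contain randomized patients who withdrew from treatment prior to receiving any IMP and patients who died". Protocol 6.4 foresees one such case among its reasons for mandatory withdrawal: "The patient has been randomized in error and has not been administered IMP". SAP 7.1 reports "the number of patients in the APTS who completed or withdrew from study", together with the size of every analysis set. Protocol 17.5 also counts completers and withdrawals in the APTS, and adds: "The number of patients who withdrew from treatment will be summarized by period and treatment group and primary reason for withdrawal". It names no set for that reason table or for the plot.

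**Listings.** Protocol 17.3: "Listings will be based on the APRS". SAP chapter 5: "Listings will be based on the APTS". SAP 7.2: the FAS. The SAP's own listings of adverse events (16.1.5, 16.1.7 to 16.1.11) and of post-baseline C-SSRS findings (16.6) use the APRS. Chapter 23 declares one change from the protocol, the number of periods to which adverse events are assigned.

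**Open-label safety.** SAP chapter 5 puts safety outputs, including exposure and concomitant medication, on the APTS for the double-blind period and on the OLES for the extension. Chapter 9, chapter 10 and sections 16.1.1, 16.1.5, 16.1.6, 16.1.8, 16.1.10 and 16.1.11 name the APTS. The 16.1.5 overview covers the open-label and follow-up periods and does not mention the double-blind period.

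**The concern.** A withdrawal table should account for everyone who withdrew. The set chosen in 7.2 is conditioned on having outcome data, so the patients it drops are those who left before contributing any. The protocol synopsis says that reasons for withdrawal will be compared between arms, and protocol 17.9.3 gives special attention to drop-outs with no follow-up data. An FAS-based table leaves out those among them who have no post-baseline assessment at all.

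Such patients are possible by design. Randomization is at Week -2 and first dose at Week 0, so a patient can leave in between. The first scheduled post-baseline UMSARS is at Week 12, and under protocol 9.6 the Withdrawal Visit takes place only where possible and can be refused by a patient who withdraws consent.

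The open-label question is separate. Protocol 6.3 bars from the OLE anyone who withdrew in the double-blind period, and consent to the OLE is optional. A denominator of all treated patients would include people who could not have an open-label event.

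**Working it through.** The plan states no figure on this point, so the check is a comparison of definitions, followed by illustrations.

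**Who can appear where**

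| Withdrawn patient | SAP 3.3 | SAP 7.1 (APTS) | SAP 7.2 (FAS) |
|---|---|---|---|
| Randomized, never dosed | withdrawn | no | no |
| Dosed, no valid post-baseline UMSARS | withdrawn | yes | no |
| Dosed, UMSARS obtained at the Withdrawal Visit (valid baseline) | withdrawn | yes | yes |

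Let *a* be the number of withdrawn patients in the first row and *b* the number in the second, with k = a + b. Of W withdrawals, 7.1 counts W - a and 7.2 shows W - a - b. The two sections therefore differ by b. The never-dosed are missing from both; their number can be recovered from 7.1 as APRS minus APTS, but not their reasons.

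**Illustration for 7.2.** Inputs: 60 patients, 40 active and 20 placebo (protocol synopsis), and 20% drop-out (SAP chapter 21). W = 60 × 0.20 = 12. The value of k is assumed, because the documents give none. The rate shown is (12 - k)/(60 - k):

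- k = 0: 12/60 = 20.0%
- k = 1: 11/59 = 18.6%
- k = 2: 10/58 = 17.2%
- k = 3: 9/57 = 15.8%
- k = 4: 8/56 = 14.3%

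By arm, with equal drop-out assumed (4/20 and 8/40, both 20.0%), one placebo patient outside the FAS gives 3/19 = 15.8%, an apparent gap of 20.0 - 15.8 = 4.2 points. One active patient outside it gives 7/39 = 17.9%.

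**Illustration for open-label adverse events.** With m patients in the OLES and 60 dosed (assumed), incidence on the APTS equals incidence on the OLES multiplied by m/60. If the planned 12 drop-outs all leave during the double-blind period, m is at most 60 - 12 = 48 and the factor at most 48/60 = 0.80. A true 20% would then show as 20% × 0.80 = 16.0% or less. If the OLES is used, as chapter 5 states, the factor is 1.

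**The case against.** The strongest reply is that little is lost and perhaps nothing. The Withdrawal Visit includes the UMSARS, may be held remotely, and its score qualifies the patient for the FAS. Never-dosed patients are outside the protocol's own APTS counts too, and no choice of set can put them in a plot timed from first dose. The SAP already lists on the APRS where safety is concerned. Chapter 5 states the OLES rule expressly, and only patients dosed in the OLE can have an event assigned to that phase (SAP 16.1.4). The percentages depend on assumed values, and the 4.2-point gap is simply what one patient in 20 is worth.

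All of this stands as a limit on size. It does not remove the inconsistency: 7.2 still tabulates a group defined in 3.3 on a set that cannot contain part of it, and 16.1.6 names the APTS for the open-label period in terms.

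A reader might infer more than the documents support:

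- *That every patient leaving before Week 12 disappears.* Those with a valid UMSARS at the Withdrawal Visit stay in.
- *That deaths or withdrawals for safety are hidden.* Deaths are reported in 16.1.7 and 16.9, adverse events leading to withdrawal are listed on the APRS in 16.1.9, and chapter 10 lists all infusions.
- *That 7.2 breaks a protocol rule on the reason table or plot.* Protocol 17.5 names no set for either. The departure from the protocol concerns listings; for the rest the conflict is within the SAP.
- *That all open-label safety percentages are diluted.* Section 16.2 uses patients with non-missing values as the denominator for other safety data.

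**Conclusion.** The point holds as a reporting inconsistency in two unrelated places.

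For 7.2, what is lost is the withdrawal reason of never-dosed patients, and of unassessed dosed patients who left for reasons other than death or an adverse event. Both groups also lose their place in the reason table and the listing, and dosed patients lose theirs in the Kaplan-Meier plot. The 7.2 reasons then fall short of the 7.1 count by the number of dosed, unassessed leavers. The size depends on k, which the documents do not give; if k is 0 there is no effect. The listing sets in 7.2 and in the chapter 5 default are undeclared departures from protocol 17.3.

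For open-label safety, two statements in the SAP conflict. Following chapter 16 literally would multiply adverse-event incidence by at most 0.80, assuming 60 dosed and the planned drop-out falling wholly in the double-blind period; following chapter 5 would not dilute it. The 16.1.5 overview omits the randomized period, although 16.1.6 supplies the detailed tables for it.

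No primary or key secondary result is touched. The point is worth correcting because programmers would otherwise have to choose between conflicting instructions.

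**What to change.** - **SAP 7.2:** use the APRS for the reason-for-withdrawal table and the listing, or the APTS with never-dosed patients shown separately. Use the APTS for the Kaplan-Meier plot.
- **SAP chapters 9 and 10 and all of 16.1:** state the APTS for the double-blind period and the OLES for the extension. Amending 16.1.5 and 16.1.6 alone would leave the same conflict in 16.1.1, 16.1.8, 16.1.10, 16.1.11 and chapters 9 and 10.
- **SAP 16.1.5:** add the double-blind period to the overview.
- **SAP chapter 5:** align the default listing set with protocol 17.3, or record the departure in chapter 23.

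The cost is SAP wording and analysis-set flags in the table programs. No new data are needed.
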